#### **4.4 Pharmacokinetic Population**

The pharmacokinetic population will consist of all subjects with at least one plasma sample collected for AKB-9778 analysis.

#### **4.5 Sub-Study Populations**

Sub-study populations include those subjects who participated in the UWF- FA, UWF- Photography, OCT-A, and ERG sub-studies, respectively.

### **5 STUDY VARIABLES AND COVARIATES**

#### **5.1 Primary Efficacy Endpoints**

The primary efficacy endpoint is the percentage of subjects with an improvement in study eye severity of diabetic retinopathy (DR) (ETDRS DRSS) of  $\geq 2$  steps at week 48 compared to baseline.

#### **5.2 Secondary Efficacy Endpoints**

Secondary efficacy endpoints include:

- Proportion of subjects with a worsening in the study eye DRSS of  $\geq 2$  steps at week 48
- Mean change from baseline in DRSS in the study eye at week 48
- Proportion of subjects with an improvement or worsening in the study eye DRSS of  $\geq 3$  steps at week 48.
- Subjects with criterion step improvement in DRSS at week 48 ( $\geq 2$  steps improvement in the study eye for patients with non-qualified fellow eye and  $\geq 3$  steps improvement on the Person scale for patients with qualified fellow eyes)
- Subjects with criterion step improvement in DRSS at week 48 ( $\geq 2$  steps improvement in the study eye for patients with non-qualified fellow eye and  $\geq 3$  steps improvement on the Binocular scale for patients with qualified fellow eyes)
- Proportion of patients developing center-involved Diabetic Macular Edema (DME) or Proliferative Diabetic Retinopathy (PDR) or PDR-related outcomes during treatment period based on Clinical Data. Due to variation in clinician criteria for reporting DME and PDR adverse events, all events will be reviewed and AEs that were not treated and were not validated in FPRC interpretation of imaging data will be censored from the results.
- Proportion of patients developing center-involved DME or PDR or worsening of  $\geq 2$  steps DRSS at week 48 based on Central Image Reading Center Evaluation
- Primary and secondary assessments in qualified fellow eyes and all qualified eyes (study eyes and qualified fellow eyes).

- Primary and secondary endpoints assessed at week 12, 24 and 36.

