### 7.2 Descriptive Statistics

For continuous variables, descriptive statistics will include the number of subjects (n), mean, standard deviation (SD), median, minimum and maximum. Categorical variables will be summarized using absolute and relative frequencies (i.e., counts and percentages). For categorical analyses, eyes that receive rescue therapy will be considered as treatment failures. Safety and PK data will be analyzed as collected.

All efficacy data will be summarized by treatment groups and overall using appropriate descriptive statistics. Summaries will be presented for both the MITT and PP populations, where applicable. Due to the small number of subjects enrolled at each center, all summaries and analyses will be performed using data pooled across centers. Unscheduled data, such as information from unscheduled visits or investigator comments, will be included in the data listings. In general, these data will be excluded from the summary tables unless otherwise specified.

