## **10.1 Primary Efficacy Endpoint Analysis**

The primary hypotheses to be tested is that AKB-9778 15 mg twice daily and AKB-9778 15 mg once daily will be superior to placebo in the improvement of DR as measured by the ETDRS severity scale change from baseline at 48 weeks. Specifically, the primary endpoint is the percentage of subjects with an improvement in study eye severity of DR (ETDRS DRSS) of  $\geq 2$  steps at 48 weeks without need for treatment of PDR or DME (by IVT, laser, or vitrectomy) in the study eye. DRSS scores used for all analyses will be obtained from final adjudicated grading by the central reading center (Fundus Photograph Reading Center for the standard field images).

The primary hypotheses will be tested in the MITT population using a Fisher's Exact Test with a 2-sided 5% significance level. AKB-9778 15 mg twice daily will be tested first. If this is found to be statistically significant, then AKB-9778 15 mg once daily will be tested for statistical significance, at the same significance level. Cochran-Mantel-Haenszel (CMH) test stratified for baseline ETDRS DRSS (levels 4, 5 and 6) will also be used for testing primary hypothesis in the MITT population. Missing data will be imputed using LOCF; baseline values will not be carried forward.

As a sensitivity analysis, primary hypothesis will be tested using Fisher's Exact test, and CMH test stratified for baseline ETDRS DRSS (levels 4, 5 and 6) on OC in the PP population.

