## **10.2 Secondary, Exploratory and Exploratory Sub-Study Efficacy Endpoint Analysis**

Secondary efficacy endpoints are summarized in Section 5.2, and involve alternative analyses of DRSS results, showing the proportion of patients who develop sight-threatening complications of DR (DME & PDR). Measures of kidney function (UACR and eGFR) are exploratory efficacy endpoints. Exploratory sub-study endpoints are derived from OCT-Angiography, Ultra-wide field fluorescein angiography, Ultra-wide field color photographs, and electroretinography. Details of these variables and their analysis are contained in separate SAPs.

Normality assumption will be tested for any endpoint of continuous nature. If normality assumption is violated, appropriate transformation and/or non-parametric analysis will be employed. Otherwise, all secondary, exploratory and exploratory sub-study endpoints of continuous nature will be analyzed using ANCOVA model, and all inferential analyses will use a 2-sided 5% significance level. For the exploratory efficacy endpoints UACR and eGFR, for internal decision-making purposes, a 1-sided 10% significance level will be used. Whenever possible, a mixed model repeated measures (MMRM) model will be utilized to analyze this data. The model will include change from baseline as the dependent variable. The p-value and 95% CI from the model is baseline parameter adjusted.

For MMRM, visit will be treated as the repeated variable within a subject. Within-subject error, an unstructured variance-covariance will be applied; in case of non-convergence, compound symmetry will be used. MMRM model for UACR and eGFR is adjusted by the baseline HbA1c, Baseline Systolic BP, log-transformed Baseline UACR, and ACEi/ARB use.

Secondary, exploratory and exploratory sub-study endpoints of a dichotomous nature will be analyzed using the same approach as outlined for the primary efficacy endpoint.

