# Note to File

**Clinical Study Protocol AKB-9778-CI-5001: PHASE 2 DOUBLE-MASKED, PLACEBO-CONTROLLED STUDY TO ASSESS THE SAFETY AND EFFICACY OF SUBCUTANEOUSLY ADMINISTERED AKB 9778 15MG ONCE DAILY OR 15MG TWICE DAILY FOR 12 MONTHS IN PATIENTS WITH MODERATE TO SEVERE NON-PROLIFERATIVE DIABETIC RETINOPATHY**

To: Statistical Analysis Plan, Final Version 27Feb2019

Date: 03-Mar-2019

Re: Criteria used to define Progression to Vision-Threatening Complications (DME and/or PDR)

---

Criteria used to define Progression to Vision-Threatening Complications (DME and/or PDR):

Qualified eyes were included as progressors if one or more of the following conditions occurred during the trial:

1. An AE of DME was entered that was either treated or was confirmed by the reading center as having either center involved retinal cyst, center involved retinal edema, center involved subretinal fluid, or central subfield thickness >300 microns.
2. An AE of PDR, NVE, NVD, or vitreous hemorrhage
3. IVT with anti-VEGF therapy or corticosteroid with indication for treatment documented as either DME or PDR
4. PRP, Grid laser, or focal laser with indication for treatment documented as either DME or PDR
5. An increase in central subfield thickness of  $\geq 20\%$  at last observation
6. DRSS score of  $>53$ , indicating PDR, at last observation

AERPIO SIGNATURE

DATE

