As a sensitivity analysis, Fisher's Exact test and CMH test stratified for baseline ETDRS DRSS (levels 4, 5 and 6) on Observed Cases (OC carrying forward pre-rescue values) in the Per Protocol (PP) population will also be performed. Secondary analyses will be performed on study eyes and all qualified eyes on derived DRSS Person and Binocular scales.

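### The SAP's analyses in all qualified eyes state neither the unit of analysis nor how two eyes of one subject are handled; if eyes are entered as independent, CMH and continuous-endpoint tests run above their nominal 5%

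*SAP*

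**What the plan says.** Subjects are randomised 1:1:1 (SAP 3.2). Under Protocol 7.3, when both eyes of a subject meet the ocular criteria, the eye with the worse DRSS becomes the study eye and the other a qualified fellow eye. A subject can therefore bring one or two qualified eyes.

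SAP 5.2 lists as secondary endpoints "Primary and secondary assessments in qualified fellow eyes and all qualified eyes (study eyes and qualified fellow eyes"). For these, SAP 10.2 says that "endpoints of a dichotomous nature will be analyzed using the same approach as outlined for the primary efficacy endpoint". That approach (SAP 10.1) is Fisher's "Exact Test with a 2-sided 5% significance level. AKB-9778 15 mg twice daily will be tested first", together with a CMH "test stratified for baseline ETDRS DRSS (levels 4, 5 and 6) will also be used for testing primary hypothesis". Continuous endpoints go to ANCOVA or, where possible, to a repeated-measures model: "For MMRM, visit will be treated as the repeated variable within a subject".

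Protocol 5.6, item 7, names three sets: all fellow eyes, qualified fellow eyes, and either eye with best response. The last gives one value per subject. SAP 5.2 keeps qualified fellow eyes and introduces all qualified eyes, and the either-eye rule does not appear. SAP 1.1 reports no change from protocol.

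**The concern.** Fisher, CMH and ANCOVA assume one independent observation per unit. Two eyes of one person share treatment, glycaemia and blood pressure, so their outcomes are likely to be positively correlated. If both enter as separate units, the variance of the arm difference is understated, p-values are too small and confidence intervals too narrow. The MMRM as written has one value per subject per visit; it does not say how a second eye at the same visit enters.

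The SAP also leaves open whether the denominator is eyes or subjects, and whether a fellow eye's CMH stratum is its own baseline level or the study eye's. Two programmers could follow the text and produce different tables. These tables repeat the primary assessment in a larger set of eyes, so a nominally significant p-value from them could be read as corroborating the primary result.

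**Working it through.** **1. The plan's own figure.** Full enumeration of the two-sided Fisher test with 45 per arm and rates of 30% v 5% gives power 86.3%, in line with the stated >85%. The inflation is 45/(1 − 0.10) = 50 per arm, as stated. Both rest on one study eye per subject and are not in question.

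**2. Is there a rule elsewhere that settles the unit?**

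- *Towards eyes.* The Note to File says "Qualified eyes were included as progressors if one or more of the following conditions occurred during the trial". SAP 7.2 says "For categorical analyses, eyes that receive rescue therapy will be considered as treatment failures", although that also fits a study-eye analysis. SAP 5.2 lists the Person and Binocular endpoints in bullets separate from all qualified eyes.
- *Towards subjects.* Most SAP 5.2 endpoints are worded as subjects or patients. The UWF color photography plan says "Secondary analyses will be performed on study eyes and all qualified eyes on derived DRSS Person and Binocular scales", which is one value per subject. Protocol 5.6 has the either-eye rule.
- *Rules that do not reach these tables.* The two-eye carry-forward rule in SAP 7.1 is for the Person and Binocular scales. The any-eye rule in SAP 11.1.1 is for ocular TEAEs.

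The unit is therefore undetermined for the pooled-eye efficacy tables.

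**3. Size of the error if eyes are treated as independent.** From the documents: 50 subjects per arm and a two-sided 5% level. Assumed: a share of subjects with two qualified eyes of 20, 30, 50 or 80%; between-eye correlation ρ of 0.3-0.7; equal true rates p of 5, 10, 20 or 30%.

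With m paired subjects per arm there are n = 50 + m eyes: 60, 65, 75 or 90. For a pair, P(both respond) = p² + ρp(1 − p). The responder-eye count per arm is the exact convolution of single eyes and pairs, and each test is applied to every possible table.

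One cell in full: 50% paired, p = 0.10, ρ = 0.5. P(both) = 0.01 + 0.5 × 0.09 = 0.055; P(exactly one) = 2 × (0.10 − 0.055) = 0.09; P(neither) = 0.855. With 75 eyes per arm, Fisher rejects 5.5% and unstratified CMH 8.6%.

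For continuous endpoints, the variance factor is 1 + ρ × 2m/n and the size is 2 × (1 − Φ(1.96/√factor)). Example: 1 + 0.5 × 50/75 = 1.33, √1.33 = 1.155, 1.96/1.155 = 1.70, so the size is 9.0%.

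Rejection rates under no treatment difference, given as ρ = 0.3 then ρ = 0.7:

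| Paired | Fisher, p = 5% | Fisher, p = 10-30% | CMH unstratified, p = 5-30% | Continuous |
|---|---|---|---|---|
| 20% | 1.4%; 2.1% | 2.9-4.0%; 3.9-5.2% | 5.6-6.2%; 7.1-7.8% | 6.2%; 7.8% |
| 30% | 1.8%; 2.8% | 3.4-4.4%; 4.9-6.2% | 6.2-6.7%; 8.3-9.0% | 6.6%; 8.8% |
| 50% | 2.6%; 4.4% | 4.3-5.1%; 6.8-7.8% | 6.3-7.4%; 9.6-10.7% | 7.4%; 10.6% |
| 80% | 3.6%; 6.6% | 5.4-6.0%; 9.0-9.8% | 7.2-8.2%; 12.0-12.6% | 8.2%; 12.4% |

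CMH with three DRSS strata, simulated with 20,000 replicates per cell, gives 5.8-8.8% at 20-30% paired and 6.6-13.0% at 50-80% paired.

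**4. Checks.** With ρ = 0, Fisher gives 1.1-3.4% and unstratified CMH 4.2-5.1%, so the excess comes from pairing and not from the tests. With ρ = 0.1-0.2, unstratified CMH gives 4.8-7.1%, a small effect. Beyond the assumed range (every subject paired, ρ = 0.9), CMH reaches about 15-18%, so the figures above are illustrations and not bounds.

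**5. Intervals.** The factors at ρ = 0.3-0.7 are 1.10-1.32 (20-30% paired) and 1.20-1.62 (50-80% paired). Taking √factor − 1, intervals that ignore pairing should be about 5-15% and 9.5-27% wider respectively.

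**The case against.** The strongest reply is that the inflation depends on a reading the SAP never commits to. Its endpoints are mostly worded per subject, and the one plan that says how all qualified eyes will be scored uses subject-level scales. The Note to File classifies eyes but names no test, and the corresponding SAP 5.2 endpoint is a proportion of patients. The SAP is also to be read with the protocol, which supplies a subject-level rule. This stands as far as it goes: a reader might infer that the SAP prescribes a naive eye-level analysis, and it does not say so. But the either-eye rule is not carried into the SAP, all qualified eyes is a different set, and the remaining text allows the eye-level reading.

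The reply on magnitude also partly stands. Pairing share and correlation are not in the documents. Fisher, the test listed first, is conservative at low rates: at the planning placebo rate of 5% it clearly exceeds 5% only at 80% paired with ρ = 0.7. Null rates of 20-30% lie above the control improvement rates quoted in Protocol 4 (6.8% and 10.9%). CMH and the continuous analyses have no such cushion.

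A reader might also extend the point to the sub-studies. The documents do not support that. The UWF-FA plan images the study eye only, and the UWF color plan puts all qualified eyes on Person and Binocular scales. The OCT-A and ERG plans image both eyes but name no pooled-eye table.

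**Conclusion.** The omission is real and worth closing before unmasking. The SAP replaces a subject-level either-eye analysis with all qualified eyes, records no change, and gives neither a unit nor an allowance for two eyes of one subject. If eyes are entered as independent, then over 20-80% pairing, correlation 0.3-0.7 and rates of 5-30%, nominal 5% tests reject about 6-13% (CMH), about 6-12% (continuous) and about 1-10% (Fisher). CMH and the continuous analyses are above 5% throughout that range; Fisher is not. At correlation 0.1-0.2 the effect is small.

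The reach is limited to the secondary efficacy tables in all qualified eyes, which Protocol 11.7 already leaves without multiplicity adjustment. The primary test, its testing order, power and sample size, the fellow-eye-only tables, the Person and Binocular endpoints and the UWF-FA sub-study are unaffected.

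**What to change.** Before unmasking, choose one option in SAP 5.2 and 10.2.

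**(a) Subject as unit.** Restore the protocol's either-eye (best response) rule or state another rule that combines the two eyes, and keep Fisher/CMH. Say how the rule works for worsening endpoints and for subjects with one qualified eye, because best response is natural only for improvement and the protocol's either-eye set is not expressly limited to qualified eyes.

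**(b) Eye as unit, subject as cluster.** For dichotomous endpoints, name one subject-clustered stratified test, for example a CMH-type score test with its variance computed from subject totals, or a subject-level permutation test. State that the stratum is the eye's own baseline DRSS level. For continuous endpoints, use a mixed model with a subject random effect and visit repeated within eye.

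Under either option, keep Fisher/CMH wherever there is one value per subject, and use the term all qualified eyes consistently with the UWF color plan. In SAP 1.1, record any departure from the protocol's either-eye analysis and, under (b), from its Fisher approach for secondary dichotomous endpoints (Protocol 11.7).

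The cost is a few lines of text and a little programming; (b) also gives somewhat wider intervals. In simulation over 20-80% pairing and correlation 0.3-0.7, the clustered score test held its size at 3.5-5.3%. At 30% v 5% its power was 93.8-98.8%, which is 0.6-2.9 points below uncorrected CMH. At 20% v 5% it was 3-14 points below, part of which is the uncorrected test's excess rejection.

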### 5.3 Exploratory Efficacy Endpoints

Change from baseline in urine-albumin-to-creatinine ratio (UACR) and estimated glomerular (eGFR) at week 12, 24, 36 and 48 in the overall MITT population and in the subgroup of subjects with renal insufficiency at baseline (UACR >30 µg/mg for UACR analysis; eGFR <90 mL/min/1.73m^2 for the eGFR analysis) is the exploratory efficacy endpoint used to investigate renal function.

For urine albumin values below the lower limit of quantitation, UACRs will be calculated using the 0.5xLLQ value. Due to the positive skewness, UACR data will be log transformed prior to analysis. The primary outcome will be percent change in geometric mean.

### 5.4 Exploratory Efficacy Sub-Study Endpoints

Exploratory efficacy sub-study endpoints include:

- Mean change from baseline in ERG parameters (LKC Composite Score; Implicit Time (ms) in 16 Td's; Amplitude Value (µV) in 16 TD's) at week 48.
- Mean change from baseline in Retinal Capillary Dropout 3x3, Retinal Capillary Dropout 6x6, FAZ Area (mmsq), Vessel Density (%), Vessel Skeleton Density 6x6 (%), Total Vessel Length 6x6 (mm) and Non-Perfusion Area 6x6 (mmsq) measured by OCT- A at week 48.
- Mean change from baseline in Ischemia Disc (%), Ischemia Macula (%), Leakage Disc (%), Leakage Macula (%) and Microaneurysm Count Macula in the regions ROI 1 and ROI 2 measured by UWF-FA at week 48.
- Subjects (Eyes) with criterion step change in DRSS on UWF-photography (Worsening ≥3, ≥2, Improvement ≥2, ≥3) at week 48

A more detailed presentation of the variables to be analyzed for these sub-studies is provided in the appended sub-study analysis plans.

### 5.5 Safety Endpoints

Safety endpoints include:

- Incidence and severity of systemic and ocular AEs
- Ocular AEs at Study eyes, all qualified eyes and unqualified fellow eyes during treatment period.
- Shift from baseline in body system assessments for the parameters general appearance, HEENT (Head, Ears, Eyes, Nose and Throat), cardiovascular, respiratory, abdomen/gastrointestinal, musculoskeletal, and dermatologic at week 12, 24, 36, 48.
- Change from baseline in vital sign measurements (SBP, DBP, HR, BMI, Weight and Temperature) at every 4 weeks.
- Change from baseline in ECG parameters (HR, PR, QRS and QTcF) at week 24, 48.
- Change from baseline in clinical laboratory assay results (blood chemistry (at every 4 weeks), hematology (at every 8 weeks), fecal occult blood test (at week 24, 36, 48), and urinalysis (at week 24, 36, 48).
- Mean change from baseline in ETDRS Best Corrected Visual Acuity (BCVA) letter score in the study eyes, all qualified eyes and unqualified fellow eyes at every 4 weeks.
- Proportion of subjects with a loss of ≥15 letters, loss of ≥10 letters and loss of ≥5 letters in BCVA compared to baseline at week 48.
- Mean change from baseline in Spectral Domain Optical Coherence Tomography (SD OCT): Central Subfield Thickness (CST) in the study eyes, all qualified eyes and unqualified fellow eyes at week 12, 24, 36, 48.

- Proportion of subjects with increase of  $\geq 100$   $\mu\text{m}$  and increase of  $\geq 50$   $\mu\text{m}$  SD OCT: CST in the study eyes, all qualified eyes and unqualified fellow eyes at week 48.
- Change from baseline in Intraocular Pressure (IOP), with additional sub-group analysis with baseline IOP  $< 16$  mmHg and baseline IOP  $\geq 16$  mmHg in the study eyes and fellow eyes at week 12, 24, 36, 48.
- Shift from baseline in Slit Lamp Biomicroscopy examination for the parameters Eyelids, Cornea, Conjunctiva, Anterior Chamber, Iris/Pupil and Lens in all qualified eyes and unqualified fellow eyes at week 12, 24, 36, 48.
- Shift from baseline in Dilated Indirect Ophthalmoscopy examination for the parameters Vitreous, Macula, Optic Nerve, and Peripheral Retina in all qualified eyes and unqualified fellow eyes at week 12, 24, 36 and 48.
- Change from baseline in Fluorescein Angiogram (FA) for the parameters total area of capillary non-perfusion, and leakage within ETDRS grid, change in fluorescein leakage from screening, NVD and NVE within 7 standard field in all qualified eyes and unqualified fellow eyes at week 24, 48.
- Shift from baseline in Fundus Photograph (FP) for the parameters clinically significant ME (ETDRS), hard exudate presence within grid, and hemorrhages and/or microaneurysms within grid in all qualified eyes and unqualified fellow eyes at 12, 24, 36, 48.

## 6 DATA PREPARATION

Except for the laboratory data (clinical laboratory assays, PK and biomarker data) and imaging data, all reported study data will be recorded on the eCRFs supplied by TrialRunners (TR) using iMedNet Electronic Data Capture (RDC). Only the Principal Investigator and authorized study staff according to the Delegation of Responsibilities log are entitled to make entries on the eCRF. Data from source documents will be entered into RDC by site personnel. The laboratory and imaging data will be incorporated into the study database electronically. The details of the laboratory data transfer can be found in the Data Transfer Agreements (DTAs) and TR's Standard Operating Procedure (SOP) on electronic data importation.

All ocular image data (fundus photographs, FA and SD-OCT) will be transmitted to the Eyekor Excelsior data platform. The Wisconsin Fundus Photograph Reading Center (FPRC) will assess all screening images to confirm subject eligibility. The FPRC will also grade all 7-field or 4-field wide color fundus photographs for DRSS, FA data, and SD-OCT data. Details are contained in the FPRC image grading charter. Ultra-wide field fluorescein angiography data will be graded by the Campane Center for Advanced Imaging at the Cole Eye Institute (CCAI) using their custom software. Details are contained in the CCAI UWF-FA charter. Electrotoretinographic data will be evaluated by LKC Technologies using their custom software. The FPRC, CCAI and LKC Technologies will store graded data in Excelsior and this data will be transferred to TR per the DTA and incorporated into the study database electronically. OCT-A and UWF-color photographs will be graded by the Boston Image Reading Center (BIRC) using their custom software. Data will be stored at BIRC and transferred TR per the DTA and incorporated into the study database electronically. Source raw images will be stored at study sites. Image grading source data will be stored at the reading centers.

All analyses outlined in this document will be carried out after the following has occurred:

- All data management requirements are met according to TR standard operating procedures, including data entry, performance of edit and validation checks, documentation and resolution of data queries, and database lock with written authorization provided by appropriate TR and Sponsor personnel;
- Protocol deviations have been identified and status defined (major/minor deviations);
- Analysis populations have been determined, and

- Randomized treatment codes have been unmasked.

